8.5 Examination of Subgroups

Descriptive statistics will be provided by alopecia subtype.

9. SAFETY EVALUATION

9.1 Overview of Safety Analysis Methods

Safety and tolerability of CTP-543 will be assessed by evaluating the following for the Safety Population:

- Adverse events
- Clinical laboratory results
- Vital signs
- ECG results
- Concomitant medications
- Physical examinations

All safety summaries will be descriptive with no statistical hypothesis testing and based on the Safety Population. Patients will be summarized according to the study drug received (i.e., as treated), should it differ from the randomized treatment arm. All safety endpoints will be listed in by-patient data listings.

9.2 Adverse Events

Adverse events will be coded using MedDRA and summarized by system organ class and preferred term. Clinically significant deteriorations in physical examination findings will be reported and summarized as adverse events.

An adverse event reported after informed consent, but before the first dose of study drug (i.e., Day 1), will be considered a pre-treatment adverse event. Treatment-emergent adverse events will be defined as any adverse event that occurs after administration of the first dose of study drug. The number and percentage of patients who report TEAEs will be summarized by system organ class and preferred term.

Treatment emergent adverse events will also be summarized by intensity as well as relationship to study drug.

Partial dates will be imputed for the purposes of defining TEAEs as follows:

- For a missing start day where the month and year are present, the start day will be set to the first day of the month, unless 1) the first day of the month is before the date of

administration of study drug and the month and year are the same as the month and year of the date of administration of study drug, and 2) the end date is on or after the date of administration of study drug or the end date is completely missing, in which case the start day will be set to the first day of administration of study drug.

- For a missing start day and month where the year is present, the start day and month will be set to January 1st, unless 1) January 1st is before the date of administration of study drug, and 2) the end date is on or after the date of administration of study drug or the end date is completely missing, in which case the start day and month will be set to that of the first date of administration of study drug.
- For a missing end day where the month and year are present, the end day will be set to the last day of the month, unless the month and year are the same as the month and year of the last contact date for the patient, in which case the end day will be set to that of the patient's last contact date.
- For a missing end day and month where the year is present, the end day and month will be set to the patient's last contact date, unless the year of the patient's last contact date is greater than the end year, in which case the end day and month will be set to December 31st.

For an entirely missing stop date (i.e. day, month, and year are missing), the TEAE will be treated as ongoing.

Patients who report the same preferred term on multiple occasions will be counted once for the preferred term: under the highest severity when summarized by severity and under the closest relationship to study drug when summarized by relationship. Missing severity or relationship will not be imputed. If a patient reports multiple preferred terms for a SOC, the patient will be counted only once for that SOC.

The number and percentage of patients who experience TEAEs will be summarized by treatment group for the following:

- By SOC and preferred term
- By severity/intensity, SOC, and preferred term
- By relationship to study drug, SOC, and preferred term
- Serious adverse events (SAEs) by SOC and preferred term
- SAEs by relationship to study drug, SOC and preferred term

- AEs resulting in discontinuation of study drug by SOC and preferred term
- AEs that result in study drug dose interruption by SOC and preferred term
- AEs that meet Grade 3-4 Common terminology criteria for adverse events (CTCAE) hematology results by system organ class and preferred term
- AEs that meet Grade 3-4 CTCAE serum chemistry results by system organ class and preferred term

By-patient listings will be provided for all AEs, SAEs, and AEs related to the study drug, as well as AEs leading to study drug withdrawal or death. A by-patient listing will also be created for any pregnancies that occur. TEAEs that result in dose interruption will also be identified.

Additionally, TEAEs will be summarized by time interval: 0 to 12 weeks, and 12 to 24 weeks. For each time interval, an incidence table will summarize only TEAEs with an onset date within the interval and a prevalence table will summarize all TEAEs that have an onset date within the interval or continue into the interval. Differences between the incidence and prevalence tables can provide insight into the duration of TEAEs as well as the recurrence of TEAEs. A preferred term for an individual patient will be reported in multiple time intervals if there are multiple adverse event reports. The denominator for each time interval will be the number of patients who received at least 1 dose of study drug within the interval. These incidence and prevalence tables will be repeated for key hematology and serum chemistry AEs categorized as CTCAE Grade 3-4 results.

9.3 Clinical Laboratory Evaluation

Observed measurements along with change from baseline for each scheduled assessment will be summarized descriptively by treatment group and visit for each clinical laboratory parameter.

Hematology parameters for patients that meet Grade 3 or Grade 4 toxicity criteria from the CTCAE v4.0 for neutrophils, platelets, and hemoglobin will be summarized for each scheduled visit and overall for all post-baseline visits. In addition, hematology parameters of interest that meet Grade 3 or Grade 4 toxicity criteria will be plotted as mean values over time. Serum chemistry parameters for patients that meet Grade 3 or Grade 4 toxicity criteria from the CTCAE v4.0 for total cholesterol, low-density lipoprotein (LDL) cholesterol, high-density lipoprotein (HDL), and triglycerides will be summarized for each scheduled visit and overall for all post-baseline visits.

Laboratory values will be converted to the project-defined unit of measurement, as applicable, before analysis. If laboratory values are recorded as above or below a threshold (i.e. “<2”, “>30”,

etc.), they will be counted as missing for continuous summaries. Abnormal, clinically significant laboratory values (per Investigator judgment) will be reported and summarized as AEs.

All laboratory parameter results will be included in by-patient data listings. Reference ranges for each clinical laboratory parameter will also be summarized in a data listing.

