13. Screening labs outside the normal range for parameters associated with potential risk for treatment under investigation. This will include but is not limited to:
  - a. Platelets  $\leq 120 \times 10^9/L$
  - b. Absolute neutrophil count  $\leq 1.5 \times 10^9/L$
  - c. Hemoglobin levels  $\leq 11$  g/dL for females, or hemoglobin levels  $\leq 12.5$  g/dL for males
14. Screening blood glucose levels of hemoglobin A1c  $\geq 6.5\%$  (48 mmol/mol).
15. Abnormal liver function at Screening, defined as  $\geq 1.5 \times$  ULN of serum alanine transaminase, serum aspartate transaminase, serum alkaline phosphatase, or total bilirubin (unless isolated Gilbert's syndrome).
16. Abnormal renal function (estimated glomerular filtration rate  $<60$  mL/min/1.73 m^2 using the MDRD equation) at Screening.
17. Any active infection at Screening, active or previous Hepatitis B or C infection, or known human immunodeficiency virus infection.
18. Vaccination with herpes zoster vaccine or any live virus vaccine within 6 weeks before Screening or during the study.
19. Positive purified protein derivative test for non-bacillus Calmette-Guérin-vaccinated patients, positive QuantiFERON®-TB Gold test, or history of incompletely treated or untreated tuberculosis.
20. History of prolonged QT syndrome or a Screening QTc interval with Fridericia's correction (QTcF)  $> 450$  msec for males or QTcF  $> 470$  msec for females.
21. History of alcohol, medication, or illicit drug abuse within 1 year before the first dose of study drug.

22. Females who are nursing, pregnant, or planning to become pregnant while in the study, and for 30 days after last dose of study medication.
23. Participation in another investigational study within the greater of 4 weeks or 5 half-lives of an investigational medication prior to screening or during the study.
24. Use of strong CYP3A4 inhibitors (such as, but not limited to clarithromycin, conivaptan, grapefruit juice, indinavir, itraconazole, ketoconazole, lopinavir/ritonavir, mibefradil, nefazodone, nelfinavir, posaconazole, saquinavir, telaprevir, telithromycin, voriconazole, or fluconazole) dosed for systemic exposure.
25. Use of strong CYP3A4 inducers (such as, but not limited to barbiturates, carbamazepine, efavirenz, glucocorticoids, modafinil, nevirapine, oxcarbazepine, phenobarbital, phenytoin, pioglitazone, rifabutin, rifampin, St. John's Wort, or troglitazone) dosed for systemic exposure.

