**Table 5: Clinical Laboratory Assessments**

Hematology	Chemistry	Serum Pregnancy
Complete blood count Absolute neutrophil count Absolute eosinophil count Platelet count White blood cell count with differential Absolute reticulocyte count Hemoglobin A1c	Alanine aminotransaminase Albumin Alkaline phosphatase Amylase Aspartate aminotransaminase Total bilirubin Direct bilirubin Indirect bilirubin Blood urea nitrogen Calcium Carbon dioxide Chloride Creatinine Creatine kinase Glucose Lipase Total protein Phosphorus Potassium Sodium Uric Acid	Human chorionic gonadotropin (females of childbearing potential only)
Serology	Lipids	Other
Hepatitis B virus Hepatitis C virus	Total cholesterol Low-density lipoprotein High-density lipoprotein Triglycerides	Tuberculosis Thyroid stimulating hormone

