### **Clinical Laboratory**

Clinical laboratory variables will be presented in 3 ways. First, change from Baseline to each scheduled assessment will be summarized descriptively. Baseline will be defined as the laboratory value obtained before the first dose of study drug on Day 1; if Day 1 values are unavailable, then values obtained at the Screening Visit will be used.

Second, treatment-emergent potentially clinically significant (PCS) laboratory values will be identified. Potentially clinically significant values are defined as those that meet Grade 3 or Grade 4 toxicity criteria from the CTCAE criteria. Treatment-emergent PCS laboratory values are those in which the baseline value is not PCS and the post-baseline value is PCS. The number and percentage of patients with treatment-emergent PCS laboratory values will be summarized by treatment group for each clinical laboratory variable.

Third, the number and percentage of patients with Abnormal, clinically significant laboratory values (per Investigator judgment) will be summarized by treatment group for each clinical laboratory variable.

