AE_TAN	14.3.1.14	Summary of CTCAE Grade 3-4 Treatment-	Safety Population	N	

		Emergent Hematology Adverse Events by System Organ Class and Preferred Term: Prevalence by Time Interval			
AE_TAO	14.3.1.15	Summary of Treatment-Emergent Adverse Events by Relationship to Study Drug, System Organ Class, and Preferred Term	Safety Population	N	
AE_TAP	14.3.1.16	Summary of Treatment-Emergent Serious Adverse Events by Relationship to Study Drug, System Organ Class, and Preferred Term	Safety Population	N	
LB_TAA	14.3.4.1.1	Summary of All Clinical Laboratory Values: Hematology	Safety Population	Y	X
LB_TAB	14.3.4.1.2	Summary of All Clinical Laboratory Values: Serum Chemistry	Safety Population	N	
LB_TAC	14.3.4.2.1	Summary of CTCAE Grade 3-4 Key Clinical Laboratory Values: Hematology	Safety Population	Y	X
LB_TAD	14.3.4.2.2	Summary of CTCAE Grade 3-4 Key Clinical Laboratory Values: Serum Chemistry	Safety Population	N	
VS_TAA	14.3.5.1	Vital Signs Summary	Safety Population	Y	

EG_TAA	14.3.5.2	12-Lead Electrocardiogram Summary	Safety Population	N	
EG_TAB	14.3.5.3	Summary of Abnormal, Clinically Significant 12-Lead Electrocardiogram Values by Treatment Group and Visit	Safety Population	Y	
EG_TAC	14.3.5.4	Summary of Clinically Notable 12-Lead Electrocardiogram Values by Treatment Group and Visit	Safety Population	Y	

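### SAP 9.3 limits the protocol's treatment-emergent Grade 3/4 laboratory count, promised for every variable, to seven variables with no baseline condition, and SAP Section 12 does not record the change

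*SAP*

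**What the plan says.** Protocol 12.4.6 (Clinical Laboratory) sets out three presentations. The first is descriptive change from baseline. The second is a threshold count: potentially clinically significant (PCS) means CTCAE Grade 3 or 4, and "Treatment-emergent PCS laboratory values are those in which the baseline value is not PCS and the post-baseline value is PCS". The commitment is then explicit: "The number and percentage of patients with treatment-emergent PCS laboratory values will be summarized by treatment group for each clinical laboratory variable". The last presentation rests on judgement rather than a threshold: "Third, the number and percentage of patients with Abnormal, clinically significant laboratory values (per Investigator judgment) will be summarized by treatment group".

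SAP 9.3 keeps the descriptive summaries for every parameter. For Grade 3 or 4 values under CTCAE v4.0 it names three hematology variables, "for neutrophils, platelets, and hemoglobin will be summarized for each scheduled visit and overall for all post-baseline visits". Under serum chemistry it names total cholesterol, LDL, "high-density lipoprotein (HDL), and triglycerides will be summarized for each scheduled visit and overall for all post-baseline visits". The matching planned tables are 14.3.4.2.1 for hematology and 14.3.4.2.2, titled "Summary of CTCAE Grade 3-4 Key Clinical Laboratory Values: Serum Chemistry".

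SAP Section 1 says that changes from the protocol-specified analyses will be documented in the SAP. Section 12 lists six; the only safety item is the revised definition of a treatment-emergent adverse event.

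**The concern.** The protocol's threshold count answers a simple safety question: how many patients in each dose group moved from below Grade 3 at baseline to Grade 3 or 4 afterwards, for each analyte measured. The SAP answers it for a short list, without the condition on the baseline value, and does not identify this as a change.

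The omitted analytes include some that the protocol treats as safety-relevant. Protocol 8.2 excludes patients for raised "serum alanine transaminase, serum aspartate transaminase, serum alkaline phosphatase, or total bilirubin" (exclusion 15) and for low estimated glomerular filtration rate (exclusion 16). Once treatment starts, none of these has a planned Grade 3-4 laboratory count. Safety is one of the two primary objectives, and the study compares three ascending doses with pooled placebo, so a count by dose group is a natural way to look for a dose-related laboratory signal.

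The title of Table 14.3.4.2.2 could hide the gap. Someone reading only the table list would expect chemistry analytes there, whereas the text of 9.3 names only lipids, which protocol Table 5 lists separately from chemistry.

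**Working it through.** The plan states no figure to reproduce, so the check is a count and a comparison of text.

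**1. Variables collected (protocol Table 5).** Hematology has 7 entries, chemistry 21 and lipids 4: 7 + 21 + 4 = 32. Hemoglobin sits inside the complete blood count entry.

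**2. Variables with a Grade 3-4 laboratory summary (SAP 9.3).** Neutrophils, platelets and hemoglobin make 3; total cholesterol, LDL, HDL and triglycerides make 4: 3 + 4 = 7.

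**3. What is left out.** Of the 21 chemistry analytes, 0 are named. In hematology, "White blood cell count with differential Absolute reticulocyte count" and the eosinophil count have no Grade 3-4 summary apart from the neutrophil part of the differential. Hemoglobin A1c is measured at Screening only (footnote 4 of the Schedule of Events), so no post-baseline count could exist for it.

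**4. The terms side by side.**

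| Element | Protocol 12.4.6 | SAP 9.3 |
|---|---|---|
| Threshold | CTCAE Grade 3 or 4 | CTCAE v4.0 Grade 3 or 4 |
| Variables | Each laboratory variable | Seven named |
| Baseline condition | Baseline below Grade 3 | None stated |
| Measure | Number and percentage of patients | To be summarized; measure not stated in 9.3 |
| Investigator-judged count per variable | Separate presentation | Left to adverse event reporting |

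The SAP does write baseline conditions elsewhere: the first three QTcF categories in 9.4.2 require a value above baseline as well as above a cut-off.

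**5. Where the baseline condition matters.** Exclusion 13 sets entry limits for platelets, neutrophils and hemoglobin. For neutrophils, the limit of 1.5 × 10⁹/L lies above the Grade 3 range of 0.5 to 1 × 10⁹/L in protocol Table 3, so few patients should start at Grade 3. Lipids have no entry limit and are first measured on Day 1. A lipid abnormality present before dosing could therefore be counted after dosing as if it had arisen on treatment.

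**6. Whether the adverse event route replaces the count.** Under protocol 10.11 the investigator classes each out-of-range result as clinically significant or not, and the significant ones are recorded as adverse events. Under 11.1.1 an abnormal value is an adverse event if it leads to discontinuation, or if the investigator judges it important enough to need treatment, a dose change or interruption, or other intervention. A Grade 3 chemistry value judged not clinically significant, and not leading to discontinuation, thus enters no Grade 3-4 table. The protocol kept the threshold count and the judgement count apart; the adverse event route preserves only the second kind.

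**The case against.** The best defence is that little is invisible. Every laboratory value is listed. Every parameter has by-visit descriptive summaries, and their minimum and maximum (SAP Section 3) show that an extreme value occurred. Grade 3-4 hematology and serum chemistry adverse events have their own tables. The narrowing can be read in 9.3 itself, and all safety analysis is descriptive. These points stand and limit the weight of the concern. They do not remove it: a maximum does not say how many patients crossed the threshold or whether they started below it, and listings leave the count to the reader.

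Two more defences stand in part. The table shells are a separate attachment and were not available; they may carry a baseline condition, and a scheduled-visit layout that includes Day 1 could show pre-existing lipid abnormalities by group. A protocol commitment should nonetheless be stated in the SAP text. The investigator-judged count largely overlaps with adverse event reporting, as both documents provide, so its loss as a separate presentation is minor.

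A reader might infer three stronger things that the documents do not support:

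- **That SAP 8.3.3 removes unscheduled draws from the overall Grade 3-4 row.** That section only lists an unscheduled or repeat visit when the planned visit is already documented. But 9.3 contrasts each scheduled visit with all post-baseline visits, which can be read as including unscheduled draws. The wording is unclear; an exclusion is not established.
- **That a Grade 3 value rising to Grade 4 on repeat would be lost.** In a combined Grade 3-4 row the patient is already counted from the planned visit. At stake is only a patient whose Grade 3-4 value appears solely at an unscheduled draw.
- **That the chemistry prevalence table has been dropped.** Table 14.3.1.14 is titled Hematology and repeats 14.3.1.12, but it follows the chemistry incidence table, and SAP 9.2 promises incidence and prevalence for both classes. The title is most likely a slip.

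**Conclusion.** The departure is real and should be fixed. A Grade 3-4 laboratory summary remains for 7 variables, with no stated baseline condition; 0 of 21 chemistry analytes have one; and none of the six entries in Section 12 covers laboratory data.

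The figure of 21 is an upper limit on the chemistry counts lost. A variable without a CTCAE grade cannot have a Grade 3 or 4 value, and the documents do not reproduce the grading tables, so the number of gradable analytes cannot be fixed from them. Nor do they allow an estimate of how many patients would go uncounted.

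The conclusion rests on the SAP text and table titles, without the shells. The baseline condition matters mainly for the four lipids. The effect is confined to descriptive safety reporting; the primary efficacy analysis is untouched. It would go too far to say that chemistry toxicity goes unreported. What is missing is the patient count by threshold that does not depend on an investigator's classification.

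**What to change.** 1. In SAP 9.3, restore the protocol's number and percentage of patients with treatment-emergent Grade 3/4 values, by treatment group, for every laboratory variable that has a CTCAE grade. State the baseline condition: below Grade 3 at baseline, Grade 3 or 4 afterwards. Extend Tables 14.3.4.2.1 and 14.3.4.2.2 to match.
2. Record in Section 12 any narrowing that remains, with a reason. This includes the investigator-judged count per variable if it is left to adverse event reporting.
3. As a clarification, state in 9.3 that the overall Grade 3-4 row uses each patient's worst post-baseline value, including unscheduled and repeat draws, and confine the 8.3.3 exclusion to by-visit summaries. Keep the scheduled-visit rows beside it, because patients with more unscheduled draws have more chances to show an abnormal value.
4. Correct the title of Table 14.3.1.14 to match SAP 9.2.

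The cost is SAP wording and minor reprogramming on data already collected. Reported abnormality rates may be slightly less favourable. No procedure or patient management changes.

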**Table 1: Schedule of Events for each Cohort**

Event	Screening	Randomization	Treatment Period					Safety Follow-Up
	Day -28 to Day -1  (Visit 1)	Day 1  (Visit 2)	Week 2, 6 (Visit 3, 5)	Week 4, 8 (Visit 4, 6)	Week 12 (Visit 7)	Week 16, 20 (Visit 8, 9)	Week 24  (Visit 10)	Week 28 (Visit 11) 
Informed consent	X							
Eligibility assessment	X	X						
Demographics	X							
Medical history	X	X						
Randomization		X						
Physical examination	X	X					X	X
Brief physical examination				X	X	X		
Height	X							
Weight	X	X		X	X	X	X	X
Pregnancy test 	X	X		X	X	X	X	
Tuberculosis test	X							
Clinical laboratory testing 	X 	X	X	X	X	X	X	X
Lipid assessment 		X			X		X	X
HBV and HCV test	X							
Pharmacokinetic blood sampling		X 	X 	X 			X 	
Pharmacodynamic blood sampling		X 	X 	X 			X 	
12-lead electrocardiogram	X	X		X	X	X	X	X
Vital signs	X	X		X	X	X	X	X
Severity of Alopecia Tool assessment 	X	X		X	X	X	X	
Photographs	X	X		X	X	X	X	
Clinician Visual Analog Scale – Severity 		X			X		X	
Clinician Global Impression of Improvement 					X		X	
Patient Visual Analog Scale - Severity		X			X		X	
Patient Global Impression of Improvement					X		X	
AASIS and exploratory questions		X					X	
Dispense study drug		X		X	X	X		
Study drug accountability				X	X	X	X	
Adverse events 	X	X	X	X	X	X	X	X
Concomitant medications 	X	X	X	X	X	X	X	X

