### **10.11. Clinical Laboratory Assessments**

Clinical laboratory assessments are presented in [Table 5](#). Clinical laboratory samples should be collected at the beginning of each clinic visit and just prior to a dose on all Study Visit Days.

The results of clinical laboratory tests conducted at the Screening Visit (and prior to dosing) must be assessed by the Investigator to determine each patient's eligibility for participation in the study. The Investigator should indicate review of the laboratory reports throughout the study by signing and dating each report.

All clinical laboratory results that fall outside the reference range will be interpreted by the Investigator as Abnormal, not clinically significant, or Abnormal, clinically significant. Laboratory results deemed Abnormal, clinically significant will be recorded as an adverse event in the eCRF and should be fully investigated and repeated for verification. Clinically significant laboratory abnormalities indicative of hematologic or other effects requiring intervention should be discussed with the Medical Monitor. Additional tests and evaluations required to establish the significance or etiology of a clinically significant abnormal result or to monitor the course of an adverse event should be obtained when clinically indicated. Whenever possible, the etiology of the clinically significant abnormal findings will be documented on the eCRF.

Any significant laboratory abnormalities that are either serious or unexpected will be promptly reported to the Sponsor. Any additional relevant laboratory results obtained by the Investigator during the course of this study will be reported to the Sponsor or designee.

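### SAP 9.3 narrows the protocol's treatment-emergent Grade 3–4 laboratory count to seven parameters, states no baseline condition, and does not record the change in Section 12

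*SAP*

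**What the plan says.** The Clinical Laboratory part of Protocol 12.4.6 commits to three displays.

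- Change from baseline at each scheduled assessment.
- Treatment-emergent potentially clinically significant (PCS) values, where PCS means CTCAE Grade 3 or 4: "The number and percentage of patients with treatment-emergent PCS laboratory values will be summarized by treatment group for each clinical laboratory variable". The baseline rule is explicit: "Treatment-emergent PCS laboratory values are those in which the baseline value is not PCS and the post-baseline value is PCS".
- Investigator judgment: "the number and percentage of patients with Abnormal, clinically significant laboratory values (per Investigator judgment) will be summarized by treatment group", again for each variable.

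SAP 9.3 keeps the first display for every parameter. For Grade 3–4 values it names three hematology parameters (neutrophils, platelets, hemoglobin). For chemistry it says "Serum chemistry parameters for patients that meet Grade 3 or Grade 4 toxicity criteria from the CTCAE v4.0 for total cholesterol" and goes on to LDL, HDL and triglycerides. Both summaries are given by scheduled visit and across all post-baseline visits together. It does not require the baseline value to be below Grade 3. Investigator-judged significant values are to be reported as adverse events (AEs), with no count by variable.

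SAP Section 1 undertakes to document departures from the protocol's analyses. Section 12 has six entries. One concerns safety (the definition of treatment-emergent AEs) and none concerns laboratory data.

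**The concern.** Safety is one of the two primary objectives, and the protocol describes this as a dose-ranging study. A reader will want to know, for each dose, how many patients developed a new Grade 3–4 liver, creatinine, muscle-enzyme or pancreatic value. The protocol promised that number, and under the SAP as written no table built from laboratory data supplies it. The protocol itself treats liver and renal function as relevant to entry (exclusion criteria 15 and 16; the former begins "Abnormal liver function at Screening, defined as" and sets enzyme and bilirubin limits).

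The missing baseline condition is a smaller matter, and it bears mainly on lipids. A patient who enters with a Grade 3–4 lipid value and stays there would count in the combined post-baseline row, although nothing emerged on treatment.

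Both are stated rules that differ from the protocol, and the section meant to record such differences does not mention them.

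**Working it through.** The point rests on comparing texts; the plan states no figure to reproduce.

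**1. Scope.** Table 5 has 7 hematology lines, 21 chemistry analytes (the column containing "Alanine aminotransaminase Albumin Alkaline phosphatase Amylase Aspartate aminotransaminase Total bilirubin" and the rest) and 4 lipids, 32 lines in all.

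| | Protocol 12.4.6 | SAP 9.3 |
|---|---|---|
| Chemistry analytes with a Grade 3–4 count | each variable (21 listed) | 0 |
| Lipids | each (4) | 4 |
| Hematology | each variable (7 lines) | 3 parameters |
| Baseline must not be Grade 3–4 | yes | not stated |
| Investigator-judged count by variable | yes | AE reporting only |
| Laboratory entries in SAP Section 12 | – | 0 of 6 |

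The SAP total is 3 + 4 = 7 parameters. The table list agrees: Tables 14.3.4.2.1 and 14.3.4.2.2 are restricted by title to key values, and no listed table shows investigator-judged laboratory values. The 21 is a count of analytes collected. CTCAE is not among the documents, so the number that have a Grade 3–4 definition cannot be settled here.

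**2. Baseline condition.** For the three hematology parameters, exclusion criterion 13 (platelets ≤120 × 10⁹/L, neutrophils ≤1.5 × 10⁹/L, hemoglobin ≤11 g/dL in females or ≤12.5 g/dL in males) makes entry at Grade 3–4 unlikely; Protocol Table 3 puts Grade 3 neutropenia at 0.5 to 1 × 10⁹/L. No listed criterion limits lipids. Criterion 13 is open-ended but concerns Screening results, and the "Lipid assessment" row of Protocol Table 1 starts on Day 1. The gap is therefore mainly the combined post-baseline row for four lipids.

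**3. What the remaining displays can show.** SAP Section 3 gives the minimum and maximum for continuous variables. A maximum above a threshold shows that at least one patient crossed it, not how many did. SAP 9.3 treats results recorded as above or below a limit as missing in continuous summaries, so such a value drops out of the maximum. SAP 8.3.3 only lists an unscheduled or repeat safety visit when the planned visit it maps to is already documented.

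**4. Illustration only.** The documents give no laboratory event rates. If the three active arms are equal, with size A, placebo is A/2 + A/2 + A/5 = 1.2A, so 4.2A = 150 and A = 35.7, about 36. Assume a Grade 3–4 rate in one variable of:

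| Assumed rate | Expected patients in 36 | P(at least 1) | P(2 or more, given at least 1) |
|---|---|---|---|
| 1% | 0.36 | 0.304 | 0.166 |
| 2% | 0.72 | 0.517 | 0.313 |
| 5% | 1.80 | 0.842 | 0.645 |

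The last column is how often a maximum would conceal that more than one patient was affected. One pre-existing lipid case counted as new adds 1/36 = 2.8 percentage points to an arm.

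**The case against.** The strongest reply is that the SAP made a reasonable selection and little is lost. Much of that stands.

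- **The seven parameters are not arbitrary.** Protocol 4.4.1 lists the parent drug's warnings. The laboratory items there are thrombocytopenia, anemia, neutropenia and lipid elevations, which correspond to the SAP's seven. This gives a plausible rationale, but the SAP does not state it, and the protocol's commitment was to every variable.
- **Pre-existing lipid cases may be visible.** Day 1 is a scheduled visit with a lipid draw, so the by-visit rows can be read as including it. A reader might infer that baseline abnormalities would pass unseen as drug effects; the text does not support that. Only the combined row is exposed.
- **The investigator-judged count is largely recovered.** Protocol 10.11 says "Laboratory results deemed Abnormal, clinically significant will be recorded as an adverse event in the eCRF", and SAP 9.2 tabulates AEs by treatment group and preferred term, with separate displays for Grade 3–4 hematology and chemistry AEs. It would be wrong to infer that this information is lost. Two reservations remain. The protocol required AE reporting in addition to the separate count. Protocol 11.1.1 also sets a narrower test for when a laboratory abnormality is an AE (discontinuation, or importance calling for intervention), though this does not show that events would go unreported.
- **The shells are not available.** Attachment A might contain a baseline filter or further rows. The SAP text and table titles give no sign of either.
- **The counts can be produced later.** Every value is listed, and Section 1 allows supplementary analyses after lock. That is true, but leaves the reader to count by hand or wait for an unplanned table.

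**Conclusion.** The concern holds as an undisclosed narrowing of a protocol-specified safety display. It is a cheap improvement to make and does not threaten the trial's conclusions. From the documents: 0 of 21 chemistry analytes have a Grade 3–4 patient count from laboratory data, no baseline condition is stated, and Section 12 records none of it. The dropped investigator-judged count is a lesser part, because AE reporting covers most of it.

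A reader might go further and infer that liver, renal or pancreatic toxicity would be concealed. The documents do not support that: every parameter is summarized at each scheduled assessment with change from baseline, every result is listed, and significant abnormalities become AEs. Nor do they show that any count would differ materially. The effect's size is unknown, and the rates in the illustration are assumptions. Efficacy and patient management are unaffected. The conclusion rests on the SAP text and table titles, without the shells.

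**What to change.** In SAP 9.3 and Tables 14.3.4.2.1 and 14.3.4.2.2, report by treatment group the number and percentage of patients with a treatment-emergent Grade 3–4 value for every Table 5 variable that has a CTCAE v4.0 grade. Apply the protocol's rule in the overall row: baseline not Grade 3–4, at least one post-baseline value Grade 3–4. At the least, add whichever of the liver tests, creatinine, creatine kinase, amylase and lipase have a grade.

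List in Section 12, with the reason, any laboratory display from Protocol 12.4.6 that is left out on purpose, including the per-variable count of investigator-judged values. If the seven were chosen to match the parent drug's warnings, say so there.

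The cost is extra rows in two planned descriptive tables, a baseline filter and a line or two in Section 12. All the data are already collected. The drawback is longer tables, in which many rows will show no patients or one.
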